**Table 23: Definition of TEAE**

Treatment group	Period covered	Definition

 
Placebo
 
Evobrutinib 25 mg QD
 
Evobrutinib 75 mg QD
 
Evobrutinib 50 mg BID
 
	12-week treatment period	
TEAEs will be defined as:
 
 
AEs starting on or after first treatment administration of any IMP (placebo or evobrutinib) during the 12-week treatment period (safety follow-up included)
 
or if it was present prior to any IMP administration but exacerbated after.
 
 
Any AE which started before study first treatment administration of any IMP (placebo or evobrutinib), but improved during treatment period, will not be counted as TEAE.

For the purpose of defining the TEAE flag, incomplete AE-related dates will be handled as follows:

- In case the onset date is missing completely or missing partially but the onset month and year, or the onset year are equal to the start of IMP then the onset date will be replaced by the minimum of start of IMP and AE resolution date.
- In all other cases the missing onset day or missing onset month will be replaced by 1.
- Incomplete stop dates will be replaced by the last day of the month (if day is missing only), if not resulting in a date later than the date of subject's death. In the latter case, the date of death will be used to impute the incomplete stop date.
- Further information collected after the cut-off for an analysis (such as a fatal outcome) may be extracted from the Safety data base and presented separately in the CSR.

### 15.1.1 All Adverse Events

AEs will be coded according to the latest MedDRA version available at the time of analysis. The severity of AEs will be graded using National Cancer Institute - Common Terminology Criteria for Adverse Events (NCI-CTCAE version 4.03) toxicity grades. AEs with missing classification concerning IMP relationship will be considered related to the IMP.

#### 15.1.1.1 3-Tier Approach

The 3-tier approach is a systematic way to summarize and analyze adverse events (AEs) in clinical trials (Crowe 2009). AEs in different tiers are analyzed using different levels of statistical analyses.

Tier 1 AEs are provided in Appendix 18.10. Other AEs will be classified into Tier 2 or Tier 3 based on the Rule-of-3. If there are 3 or more subjects with the reported term in any treatment group, that term will be included in Tier 2. Otherwise, it will be included in Tier 3.

The Tier 1 and Tier 2 AEs will be assessed with the number and percentage of subjects having at least one occurrence, as well as the difference with placebo and corresponding 95% CI for between-group comparison. For the difference in crude rates, the CIs will be based on MN method (Miettinen 1985). No multiplicity adjustment will be applied.

The tier 3 AEs will be assessed via summary statistics and risk differences.

For each comparison of evobrutinib group with placebo, forest trees for Tier 1 and Tier 2 AEs will be provided as well, displaying the incidence rate and associated 2-sided 95% CI of difference.

#### 15.1.1.2 Overview of TEAEs

Two summary tables of TEAEs will be provided as described in Table 24.

**Table 24: Summary Tables of TEAEs**

Summary	Modalities
Overview of TEAEs	
 
• Any TEAE
 
• IMP related TEAE
 
• Serious TEAE
 
• IMP related serious TEAE
 
• TEAE with NCI-CTCAE grade 1
 
• IMP related TEAE with NCI-CTCAE grade 1
 
• TEAE with NCI-CTCAE grade 2
 
• IMP related TEAE with NCI-CTCAE grade 2
 
• TEAE with NCI-CTCAE grade 3
 
• IMP related TEAE with NCI-CTCAE grade 3
 
• TEAE with NCI-CTCAE grade 4
 
• IMP related TEAE with NCI-CTCAE grade 4
 
• TEAE leading to death
 
• IMP related TEAE leading to death
 

Overview of TEAEs Actions: 
 
• Change in dose,
 
• Administration of medication,
 
• Procedure,
 
• Study termination
 
	
 
• TEAE with no change of dose
 
• IMP related TEAE with no change of dose
 
• TEAE leading to dose reduction
 
• IMP related TEAE leading to dose reduction
 
• TEAE leading to dose increase
 
• IMP related TEAE leading to dose increase
 
• TEAE leading to interruption of IMP
 
• IMP related TEAE leading to interruption of IMP
 
• TEAE leading to withdrawal of IMP
 
• IMP related TEAE leading to withdrawal of IMP
 
• TEAE leading to administration of concomitant medication
 
• IMP related TEAE leading to administration of concomitant medication
 
• TEAE leading to concomitant procedure
 
• IMP related TEAE leading to concomitant procedure
 
• TEAE leading to study termination
 
• IMP related TEAE leading to study termination
 

### 15.1.1.3 Tabulation of Adverse Events by SOC and PT

The TEAE tables to be prepared are listed in [Table 25](#).

**Table 25: TEAE Tables to be produced**

	Overall frequency	By primary SOC and PT	By PT only	By primary SOC, PT and worst grade
Overview of TEAEs	✓	NA	NA	NA
Overview of TEAEs actions	✓	NA	NA	NA
All TEAEs	✓	✓	✓	✓
IMP-related TEAEs	✓	✓	✓	✓
AEs of Special Interest (AESI)	✓	✓		
IMP-related AESIs	✓	✓		
Serious TEAEs	✓	✓		
IMP-related serious TEAEs	✓	✓		
Non-serious TEAEs*	✓	✓		
TEAEs leading to death	✓	✓		
IMP-related TEAEs leading to death	✓	✓		
TEAEs leading to withdrawal of IMP	✓	✓		
TEAEs leading to study termination	✓	✓		
EAIR	✓	✓		

(\*): A table with all non-serious TEAEs will be first provided and then only TEAEs exceeding a frequency of 5% in at least one of the treatment groups (> 5%), by SOC and PT will be provided.

**Specific rules for SOC/PT tabulation**

All AEs recorded during the trial (ie assessed from signature of informed consent until the end of the Follow-up/End of Trial visit) will be coded according to the MedDRA and assigned to a SOC and PT.

SOC terms will be sorted alphabetically. The combined dose of evobrutinib (25 mg QD, 75 mg QD and 50 mg BID) will be computed and displayed in the table. PTs within each SOC will be sorted by descending frequency of this combined dose of evobrutinib, and then alphabetically if multiple PTs have the same frequency.

If a subject experiences more than one occurrence of the same TEAE during the trial, the subject will be counted only once for that treatment (the worst severity and the worst relationship to trial treatment will be tabulated).

In case a subject had events with missing and non-missing grades, the maximum of the non-missing grades will be displayed.

Exposure adjusted incidence rates (EAIR) are calculated as number of subjects with TEAE divided by the sum of the individual times of all subjects in the safety population from start of treatment to first onset of TEAE or end of treatment period, whichever occurs first. The incidence rate multiplied with 1000 would give the number of TEAEs expected in 1000 subjects within 1 year. EAIR of TEAEs will be presented by SOC and PT.

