#### Trial Duration

Total duration of subject participation is approximately 5 months (approximately 20 weeks), which includes:

- Screening: 28 days (4 weeks)
- Treatment: 84 days (12 weeks)
- Safety Follow-up: 28 days (4 weeks).

The trial will be conducted on an outpatient basis. Subjects will attend clinic visits at regular intervals as indicated in the Schedule of Assessments (Table 1).

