#### **Safety Follow-up Period**

Subjects will enter the Safety Follow-up Period after the Week 12/End of Treatment Visit. For subjects who discontinue the Treatment Period (discontinue IMP) during the main study, an End of Treatment/Early Withdrawal Visit should occur with the subject then entering the Safety Follow-up Period. The Safety Follow-up Visit/End of Trial visit is scheduled 28 days (+ 5-day window) after the End of Treatment/Early Withdrawal Visit.

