### 6.2 Final Analysis

The final analysis will be triggered when 100% of subjects randomized either complete the Week 12 visit or discontinue prematurely prior to Week 12, the protocol violations are determined, and the database is locked. All data collected from the Safety follow-up visit during the double-blind 12-week treatment period will be included.

Data collected during the OLE period from earlier versions of the protocol will not be part of the Final analysis for the 12 Weeks treatment period but be summarized separately (See Section 7).

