**Table 6: Protocol Deviations**

Period covered for protocol deviations reporting	Treatment Group	Observation Period	Analysis Set
12-week treatment period	
 
• Placebo
 
• Evobrutinib 25 mg QD
 
• Evobrutinib 75 mg QD
 
• Evobrutinib 50 mg BID
 
	First dose of 12-week treatment period up to last observed dose during the 12-week treatment, (safety follow-up posterior to the 12-week treatment period included)	ITT

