**Table 22 : Data Handling for Safety Analysis**

Population	Period covered	Treatment groups	Data to be analyzed
SAF	12-week treatment period	
 
Placebo
 
Evobrutinib 25 mg QD
 
Evobrutinib 75 mg QD
 
Evobrutinib 50 mg BID
 
	All Data collected during the 12-week treatment period, safety follow-up included
Subjects with at least 1 dose during OLE	OLE period only	
 
Placebo/Evobrutinib 50 mg BID
 
Evobrutinib 25 mg QD/Evobrutinib 50 mg BID
 
Evobrutinib 75 mg QD/Evobrutinib 50 mg BID
 
Evobrutinib 50 mg BID/Evobrutinib 50 mg BID
 
	Data from OLE period only including all Safety follow-up data posterior to OLE (Safety follow-up / End of Study)

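### The exposure-adjusted incidence rate counts first TEAEs from the 4-week safety follow-up but stops person-time at the end of treatment

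*SAP*

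**What the plan says.** SAP 15.1.1.3 (Specific rules for SOC/PT tabulation) divides the number of subjects with a TEAE by summed individual times, each running "from start of treatment to first onset of TEAE or end of treatment period, whichever occurs first". It then gives an interpretation: "The incidence rate multiplied with 1000 would give the number of TEAEs expected in 1000 subjects within 1 year". Table 25 plans EAIR overall and by SOC and PT.

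The numerator takes its meaning from SAP Table 23, where a TEAE is an event starting on or after first IMP "during the 12-week treatment period (safety follow-up included"), or one present earlier that worsened after IMP. The EAIR text does not restrict the count to onsets on treatment.

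The follow-up is placed after treatment. SAP Table 6 has "safety follow-up posterior to the 12-week treatment period included". Protocol 5.1 states "Subjects will enter the Safety Follow-up Period after the Week 12/End of Treatment Visit", and lists 84 days of treatment separately from "Safety Follow-up: 28 days (4 weeks"). SAP 10.1 tabulates completing the treatment period and completing the follow-up as separate milestones.

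One sentence, in SAP 6.2, is looser: "All data collected from the Safety follow-up visit during the double-blind 12-week treatment period will be included". It does not define the EAIR window.

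**The concern.** An incidence rate needs events and time at risk from the same window. Here a subject whose first TEAE starts in follow-up counts as an event, yet no subject contributes any follow-up time. The rate for such a term is overstated against a rate that uses the full window, and it no longer describes the on-treatment period either.

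What is at stake is the absolute rate. EAIRs are read as events per 1000 person-years and set beside rates from other studies, and the SAP itself invites the annual reading. A term with no first onset in follow-up is unaffected: its EAIR as written equals its on-treatment rate.

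**Working it through.** The documents state no EAIR, TEAE rate or number of OLE entrants, so there is no planned figure to reproduce.

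**Inputs**
- From the documents: treatment T = 84 days and follow-up F = 28 days (Protocol 5.1); about 11% dropout and noncompliance over 12 weeks, a planning figure (SAP 8.2.1); about 90 subjects per arm.
- Assumed: constant hazard λ on treatment, follow-up hazard hλ, share o entering the OLE, and the day of early stopping.

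**Formulas** (time to first TEAE)
- On-treatment risk pT = 1 − exp(−λT); on-treatment person-time D_T = pT/λ.
- Follow-up risk pF = exp(−λT)(1 − exp(−hλF)); D_F is the follow-up person-time to first TEAE.
- Rate as written = [pT + (1 − o)pF]/D_T.
- Ratio to the full-window rate = (D_T + (1 − o)D_F)/D_T.
- Ratio to the on-treatment rate = [pT + (1 − o)pF]/pT.

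**1. Completers, equal hazard (h = 1, o = 0), against the full-window rate**

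| 12-week risk | Ratio |
|---|---|
| 0.1% | 1.333 |
| 20% | 1.287 |
| 50% | 1.206 |

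The rare-term limit is (84 + 28)/84 = 1.333.

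**2. Rare terms, against the on-treatment rate**, (84 + 28h)/84

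| h | Ratio |
|---|---|
| 0 | 1.00 |
| 0.5 | 1.17 |
| 1 | 1.33 |
| 1.5 | 1.50 |

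**3. OLE entry** (rare terms, h = 1). The SAP Table 22 entry for OLE subjects reads "Data from OLE period only including all Safety follow-up data posterior to OLE", so their later follow-up falls outside the 12-week table. The ratio is (84 + 28(1 − o))/84: 1.30, 1.25 and 1.17 for o = 10%, 25% and 50%.

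**4. Early stopping** (rare terms, h = 1). If 11% stop on day s, mean treatment time is 0.89 × 84 + 0.11s, and each subject still has 28 days of follow-up.
- s = 70: 82.46 days, ratio 110.46/82.46 = 1.340.
- s = 14: 76.30 days, ratio 104.30/76.30 = 1.367.

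**5. Between arms** (rare terms, h = 1, stopping at day 28).
- 5% stopping: mean treatment time 0.95 × 84 + 0.05 × 28 = 81.2 days, ratio 109.2/81.2 = 1.345.
- 20% stopping: 0.80 × 84 + 0.20 × 28 = 72.8 days, ratio 100.8/72.8 = 1.385.
- The rate ratio between arms shifts by 1.385/1.345 = 1.03.

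**6. Illustrative arm of 90 completers**, 4 first onsets on treatment and 2 in follow-up, each at mid-window (days 42 and 98).
- Person-years to day 84: (86 × 84 + 4 × 42)/365.25 = 20.24.
- Person-years to day 112: (84 × 112 + 4 × 42 + 2 × 98)/365.25 = 26.75.
- As written: 6/20.24 = 296 per 1000 person-years.
- Matched 16-week window: 6/26.75 = 224.
- On treatment only: 4/20.24 = 198.

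With 6 onsets on treatment and none in follow-up, person-years to day 84 are (84 × 84 + 6 × 42)/365.25 = 20.01. The rate as written is then 6/20.01 = 300, equal to the on-treatment rate.

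**The case against.** The best counter-argument is that the treatment period in the EAIR sentence is a reporting label that already includes follow-up. SAP Section 15 says its data selection applies to all safety endpoints, and Table 22 puts follow-up data in the row labelled as the 12-week treatment period. On that reading the windows match. It is possible, but it is not what the sentence says. Tables 6, 22 and 23 each add follow-up explicitly when it is meant, and those additions would be redundant if the bare term covered it. The EAIR sentence has no such addition, so a programmer following it would censor at the end of treatment.

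A second objection is that the early-stopping figures need the period to end when the subject stops IMP, not at nominal Week 12. They do depend on that. Protocol 5.1 (Safety Follow-up Period) supports it by equating discontinuing the Treatment Period with discontinuing IMP.

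Three further points stand. The size is not fixed by the documents, and 1.33 needs a rare term, an unchanged hazard off drug and no OLE entry. The EAIR counts subjects with a first event, so the annual sentence is loose even with matched windows. Finally, the EAIR is descriptive: no efficacy result or hypothesis test uses it, the Tier 1 and Tier 2 comparisons in 15.1.1.1 use crude rates, and TEAE listings would allow recalculation.

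**Conclusion.** The concern holds. Read literally, the SAP gives a rate whose numerator window is about four weeks longer than its denominator window. This is an error in the definition, not merely missing detail.

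For rare terms in completers with an unchanged hazard, the overstatement against the full-window rate is about one third. It is smaller for common terms or with OLE entry, and slightly larger with early stopping. Against the on-treatment rate it can be nil or reach one half, depending on a follow-up hazard that the documents do not give.

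The damage is mainly to absolute rates. In the example with unequal stopping, the between-arm ratio moved by about 3%. The mismatch should be corrected, but it does not threaten the trial's efficacy conclusions or its crude-rate safety comparisons.

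**What to change.** In SAP 15.1.1.3, define the at-risk window once and use it for both parts of the rate. Either option works:

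- End person-time at the earliest of first TEAE onset, the Safety Follow-up visit, last contact and first OLE dose, and count TEAEs over that same window.
- Keep the present person-time and count in the EAIR only TEAEs with onset by the end of treatment, with that date defined for subjects who stop early.

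Align the wording of SAP 6.2 so that the follow-up visit is not described as falling within the treatment period. It would also help to reword the annual interpretation as subjects with a first TEAE.

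The cost is one sentence in 15.1.1.3, the wording edits and one censoring date (or one onset filter) in the program. No new data are needed. Reported rates will fall for terms with follow-up onsets. Under the first option they also fall for terms with none, because the denominator grows: in the 6-and-0 example, person-years become (84 × 112 + 6 × 42)/365.25 = 26.45 and the rate goes from 300 to 6/26.45 = 227 per 1000.

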### **Subject data listings**

TEAEs will be also listed by treatment group and subject. A listing of TEAEs leading to withdrawal of IMP, a listing of TEAEs leading to study termination, if any, will be provided as well.

#### **15.1.1.4 Adverse Events of Special Interest**

AESIs will be summarized by SOC and PT as stated in [Table 25](#). CCI [REDACTED]

## **15.2 Deaths, Other Serious Adverse Events, and Other Significant Adverse Events**

### **15.2.1 Deaths**

A summary of deaths will be provided including (clinicaltrials.gov requirement):

- Number and percentage of (all) deaths
- Number and percentage of the primary cause of death (categories: disease progression, adverse event, unknown, other)

The tabulation of TEAEs leading to death is described in [Section 15.1.1.2](#). A listing of deaths, if any, will be provided.

In case there is no death in the trial, only the summary of death required by clinicaltrials.gov will be performed, neither tabulation of TEAE leading to death will be edited, nor the listing of death.

### **15.2.2 Serious Adverse Events**

The tabulation of serious TEAEs is described in [Section 15.1.1.2](#). A subject listing of serious TEAEs will be provided.

### 15.3 Clinical Laboratory Evaluation

The following laboratory parameters will be measured during the trial as part of the safety evaluation:

- Hematology
- Biochemistry, including the following supplementary liver function tests (LFT):
  - Aspartate aminotransferase,
  - Alanine aminotransferase,
  - Alkaline phosphatase,
  - $\gamma$ -Glutamyl-transferase,
  - Bilirubin (total),
- Urinalysis
- Coagulation
- Lipid panel
- Hepatic panel (restricted to subjects for whom above AST or ALT withdrawal criteria are met and who permanently discontinue dosing due to elevated LFTs)

The clinical laboratory safety tests to be measured in this trial are provided in the protocol (refer to Section 7.4.3 Table 10 of the CTP). Parameters from the Section 7.4.3 of the CTP to be summarized and listed in the TLFs are provided in Appendix 18.8.

All laboratory data results will be presented using international system of units (SI).

Continuous protocol-specified clinical laboratory findings (hematology, biochemistry, urinalysis, coagulation, lipid panel, hepatic panel) will be summarized by treatment using descriptive statistics over time (see Section 9) separately for 12-week treatment period and OLE. The descriptive statistics will be presented as follows:

- The baseline will be presented first
- Then, when applicable, each scheduled time point will be presented on subjects who have reached this time point: absolute values, CFB and percent CFB will be displayed.

Laboratory results will be classified according to NCI-CTCAE Version 4.03 as provided by the central laboratory. In case a laboratory parameter has bi-directional toxicities (eg Potassium) both directions will be presented for the given parameter (ie Potassium Low and Potassium High).

Laboratory results containing a modifier such as “<” or “>” will be handled case by case for summary statistics and will be reported both as collected in the database and imputed in subject

data listings. Decision for each laboratory parameter will be documented in a Note-to-File prior to the database lock.

A shift table of baseline versus post-baseline based on the worst NCI-CTCAE grade will be presented by treatment group for hematology and biochemistry.

Subject data listings will be provided, with a flag for abnormal values, along with corresponding normal ranges:

- Laboratory gradable parameters part of NCI-CTCAE will be presented according to the categories based on normal ranges along with the grade. Abnormal values will be flagged according to the direction of toxicity as detailed in Appendix 18.8 (eg, for a parameter such as Potassium Low, only values below the LLN will be flagged).
- Laboratory parameters that are not part of NCI-CTCAE will be presented according to the categories based on normal ranges: below normal limits (Low), within normal limits (Normal), and above normal limits (High). Values that are either above ULN or below LLN will be flagged.

Boxplots of the laboratory values by treatment group and time point will be provided for the following parameters of Table 26:

**Table 26: Laboratory Parameters**

Category	Laboratory parameter	Conventional Unit	SI Units
Hematology	Hemoglobin	g/dL	g/L
	Reticulocyte count	10  /μL	10  /L
	White blood cell count	10  /μL	10  /L
	Neutrophil count	10  /μL	10  /L
	Lymphocyte count	10  /μL	10  /L
	Platelet count	10  /μL	10  /L
Biochemistry	Albumin	g/dL	g/L
	Alanine aminotransferase (ALT)	U/L	U/L
	Aspartate aminotransferase (AST)	U/L	U/L
	Gamma-glutamyl transferase (GGT)	U/L	U/L
	Alkaline phosphatase	U/L	U/L
	Total bilirubin	mg/dL	μmol/L
	Amylase	U/L	U/L
	Lipase	U/L	U/L
	Creatinine	mg/dL	μmol/L
	Blood urea nitrogen (BUN)	mg/dL	mmol/L

Boxplots for all laboratory parameters will be displayed using the unit of measurement. If consistent with BOA standards, the ULN and LLN will be added to the lab parameter boxplot, for any lab parameter where the normal range is the same for all subjects in the analysis set.

Listings of individual data with a flag for abnormal values will be provided, along with corresponding normal ranges.

In this study, clinically significant lab abnormalities were recorded as adverse events. In lieu of a listing of clinically significant lab abnormalities for each domain, the following by-subject lab value listings will be provided:

- Listing of Grade  $\geq 3$  hematology values
- Listing of Grade  $\geq 3$  biochemistry values
- Listing of urinalysis values with Grade  $\geq 3$ , value  $\geq 2$  times ULN (excluding values for Specific Gravity or pH parameters), or an increase of “++” for non-gradable parameters when applicable.

**CCI**

## 15.4 Vital Signs

Vital signs (height (m), weight (kg), BMI (kg/m^2), body temperature (°C), SBP (mmHg), DBP (mmHg), respiratory rate (breaths/min) and pulse rate (beats/min)) will be summarized by treatment group using descriptive statistics (see Section 9).

The descriptive statistics will be presented as follows:

- The baseline will be presented first
- Then each scheduled time point will be presented on subjects who have reached this time point: absolute values, CFB and percent CFB will be displayed (except Height and BMI which are only collected at baseline).

Body temperature, SBP, DBP, respiratory rate and pulse rate will be analyzed with shift tables of maximum CFB using the categories defined in [Table 27](#):

**Table 27: Vital Signs Categories**

Parameter	Unit	Shift	Baseline categories	Post-baseline categories (absolute change)
Temperature	°C	Increase	<37 / ≥37 - <38 / ≥38 - <39 / ≥39 - <40 / ≥40	≤0* / >0 - <1 / ≥1 - <2 / ≥2 - <3 / ≥3
Pulse rate	bpm	Increase and decrease	<100 / ≥100	≤0* / >0 - ≤20 / >20 - ≤40 / >40
SBP	mmHg	Increase and decrease	<140 / ≥140	≤0* / >0 - ≤20 / >20 - ≤40 / >40
DBP	mmHg	Increase and decrease	<90 / ≥90	≤0* / >0 - ≤20 / >20 - ≤40 / >40
Respiratory rate	breaths/min	Increase and decrease	<20 / ≥20	≤0* / >0 - ≤5 / >5 - ≤10 / >10

\* This category will include the subjects with no changes or decrease/increase in the increase/decrease part of the table respectively.

A listing of maximum CFB and a listing of all vital signs data will be provided.

